- Characterization of physical performance levels in patients considered for kidney transplantation.
- Identification of changes in physical performance post-transplant.
- Comparison of frailty progression in patients eligible vs. ineligible for the transplant list.

7. Ethical Considerations

- Informed consent will be obtained from all participants.
- Approval from the institutional review board will be secured.

8. Conclusion

This study will provide crucial insights into the implications of physical frailty, as assessed by SPPB, in the context of kidney transplantation. The findings will help in formulating intervention strategies to improve patient outcomes.

Methodology (Detailed)

SPPB Assessment Procedure:

The **Short Physical Performance Battery (SPPB)** evaluates lower extremity function through three components, each scored on a standardized scale. The total SPPB score ranges from **0 to 12**, with higher scores indicating better physical performance and lower frailty levels.

Components and Scoring:

1. Balance Tests (Maximum score: 4 points)

- **Side-by-side Stand:**
 - Held for 10 seconds → 1 point
 - Unable to hold for 10 seconds → 0 points
 - **Semi-tandem Stand:**
 - Held for 10 seconds → 1 point
 - Unable to hold for 10 seconds → 0 points
 - **Tandem Stand:**
 - Held for 10 seconds → 2 points
 - Unable to hold for 10 seconds → 0 points
- Overall balance score:* Sum of these tests, capped at 4 points.

2. Gait Speed (Maximum score: 4 points)

- Time to walk 4 meters (standardized corridor):
 - **> 4.82 seconds:** 0 points
 - **3.00 – 4.82 seconds:** 1 point
 - **< 3.00 seconds:** 2 points

3. Repeated Chair Stands (Maximum score: 4 points)

- Time to rise from a chair 5 times:
 - **> 16.7 seconds:** 0 points
 - **11.2 – 16.7 seconds:** 1 point
 - **< 11.2 seconds:** 2 points

Note: For all components, the best possible score per sub-test is reached if the participant can perform the task within the ideal time or balance parameters.

Scoring Interpretation:

Total Score	Frailty Status
0–6	Frail
7–9	Pre-frail
10–12	Robust/Non-frail (Normal physical performance)

Assessment Protocol:

- **Baseline:** During initial transplant evaluation, clinicians will perform the SPPB following standardized procedures.
- **Follow-up:** The same assessments will be repeated at annual intervals for listed patients and at 6 and 12 months post-transplant.

UNIVERZITNÁ NEMOCNICA MARTIN
[name]
TRANSPLANTAČNO-NEFROLOGICKÉ ODDELENIE

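### The tandem stand scores 2 or 0 with nothing between, so a balance score of 3 is practically unreachable and a near-miss costs 2 SPPB points

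*Protocol*

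**What the plan says.** All of this is in the Protocol, Methodology (Detailed), Components and Scoring, unless another section is named.

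- The balance component is headed "Balance Tests (Maximum score: 4 points". Side-by-side and semi-tandem each follow the rule "Held for 10 seconds → 1 point". Tandem follows "Held for 10 seconds → 2 points". For all three, a shorter hold falls under "Unable to hold for 10 seconds → 0 points".
- The balance score is the "Sum of these tests, capped at 4 points".
- Gait and chair stands are each printed with three time bands worth 0, 1 and 2 points, under the headings "Gait Speed (Maximum score: 4 points" and "Repeated Chair Stands (Maximum score: 4 points".
- The three components are introduced as "each scored on a standardized scale".
- Scoring Interpretation cuts the total at 0–6 (frail), 7–9 (pre-frail) and 10–12 (robust).
- Section 3 makes SPPB change before and after transplantation the primary objective. Section 5 plans paired tests and mixed models on the score, and Kaplan-Meier analysis by frailty status. The Detailed Description uses the classes to describe how common frailty is and how it evolves.
- Under Assessment Protocol, the data-recording item requires the scores to be stored. It does not mention hold times.

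**The concern.** Tandem carries as many points as the whole printed gait or chair-stand scale, but it is the only one of the three without a middle level. Every other printed threshold moves the total by 1 point; the tandem threshold moves it by 2. A patient who holds for 9.9 seconds scores the same as one who cannot take up the stance, and 2 points below one who reaches 10.0.

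Two things are at stake. First, the primary measure is change in this score within a patient, and partial gain or loss of tandem balance between visits is either invisible or counted as 2 points. Second, the pre-frail class is only three points wide (7, 8, 9), so a 2-point step crosses a class boundary from more starting totals than a 1-point step does.

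The timing matters too. If only 0 or 2 is stored, no later analysis plan can re-score partial holds, and a pre-transplant visit cannot be repeated.

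**Working it through.** **Inputs (Protocol, Components and Scoring; Scoring Interpretation).** Side-by-side S = 0 or 1; semi-tandem M = 0 or 1; tandem T = 0 or 2. Balance = min(4, S + M + T). Gait g and chair c: 0–2 each as printed, 0–4 each as headed. Classes: 0–6, 7–9, 10–12.

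**1. The stated maximum.** 1 + 1 + 2 = 4, which agrees with the heading. The sum cannot exceed 4, so the cap never acts.

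**2. Reachable balance scores.** There are 2 × 2 × 2 = 8 hold/fail patterns. A score of 3 arises in two of them, (S, M, T) = (1, 0, 2) and (0, 1, 2). Both require holding the tandem while failing an easier stand. Assuming that a patient who holds a harder stand also holds the easier ones, four patterns remain:

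| S | M | T | Balance |
|---|---|---|---|
| 0 | 0 | 0 | 0 |
| 1 | 0 | 0 | 1 |
| 1 | 1 | 0 | 2 |
| 1 | 1 | 2 | 4 |

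**3. Effect of a tandem near-miss on class.** Balance drops from 4 to 2, so compare the class of 4 + g + c with the class of 2 + g + c. The class changes only when the total before the loss is 7, 8, 10 or 11, that is, when g + c = 3, 4, 6 or 7.

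| g + c | Total before → after | Combinations, 0–2 as printed | Combinations, 0–4 as headed |
|---|---|---|---|
| 3 | 7 → 5 | 2 | 4 |
| 4 | 8 → 6 | 1 | 5 |
| 6 | 10 → 8 | not reachable | 3 |
| 7 | 11 → 9 | not reachable | 2 |
| **Sum** | | **3 of 9** | **14 of 25** |

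**4. With a 1-point intermediate level.** A near-miss now takes balance from 4 to 3. The class changes only at 7 → 6 (g + c = 3) and 10 → 9 (g + c = 6). As printed: 2 of 9. As headed: 4 + 3 = 7 of 25. All five balance scores, 0 to 4, become reachable in ordered patterns.

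These counts give every gait/chair combination equal weight. The Protocol gives no score distribution and no frequency of holds near 10 seconds, so they are not shares of patients.

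**The case against.** The rule is not self-contradictory. The three stands add up to the stated 4 and the rule can be applied as written; it is a coarse item, not an unusable one. That stands, and it limits the weight of the point.

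Any cut-off creates a cliff, and graded credit adds a threshold at the minimum hold. This also stands. The crossings in the working are divided, not abolished: at the new lower threshold, 3 to 2, the class changes when g + c = 4 or 7. That is 1 of 9 as printed and 5 + 2 = 7 of 25 as headed, and 2 + 1 = 3 and 7 + 7 = 14. The gain is that no single threshold carries all of them, and that partial holds become visible.

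Three stronger readings are tempting, and the Protocol does not support them.

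- *More than half of patients near the threshold would change class.* The 14 of 25 is an unweighted count of combinations, and it assumes a 0–4 range that the printed gait and chair bands do not deliver.
- *No patient who misses the tandem can leave the frail class.* As printed, 2 + 2 + 2 = 6, so this is true on the page. It follows from gait and chair stopping at 2 points under headings of 4, which is a separate contradiction. If those bands reached 4, the same patient could total 2 + 4 + 4 = 10, which is robust.
- *The rule demonstrably adds noise and produces false frailty transitions.* That would need test-retest or hold-time data, and the Protocol has none. The score tables show lost resolution and a doubled step; the rest is inference.

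**Conclusion.** The point holds as a weakness of measurement, worth correcting but not in itself a bar to the study. With stands ordered by difficulty, balance takes the values 0, 1, 2 and 4, and a tandem hold just under 10 seconds costs 2 points where every other printed threshold costs 1. In unweighted combinations a near-miss changes the frailty class in 3 of 9 (points as printed) or 14 of 25 (0–4 as headed), against 2 of 9 and 7 of 25 with an intermediate level.

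This rests on two assumptions: the ordering of the stands, without which a 3 is formally possible in two of eight patterns; and, for the figures out of 25, that gait and chair will be corrected to reach 4. The issue would survive that correction, because balance already reaches its stated maximum and its lines could be left as they are.

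**What to change.** When the scoring table is reconciled as a whole:

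1. Give tandem three levels: 2 points for the full 10 seconds, 1 point for a partial hold at or above a pre-set minimum, and 0 below that. Take the minimum from the standardized SPPB procedure and cite it. The Protocol names no scoring sheet and the figure cannot be derived from its text.
2. Record tandem hold time in seconds at every visit, so that scores can be checked and re-derived.

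The cost is one amended scoring line and one data field. The stance has to be timed already, so no procedure is added. Deleting the cap is editorial, since it changes no score.

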UNIVERZITNÁ NEMOCNICA MARTIN
[name]
TRANSPLANTAČNO-NEFROLOGICKÉ ODDELENIE
TRANSPLANT-NEPHROLOGY DEPARTMENT

STUDY TITLE

**Physical Performance Assessment in Kidney
Transplant Evaluation Using the Short Physical
Performance Battery (SPPB)**

(FRAIL-KTx)

NCT number:

In Martin, Slovakia 9th JULY 2025

Brief Description

This prospective cohort study investigates physical frailty, assessed by the Short Physical Performance Battery (SPPB), in patients evaluated for kidney transplantation. The study aims to compare SPPB scores before listing, annually during the waiting period, and after transplantation at 6 and 12 months. It also includes a control group of dialysis patients not eligible for transplantation to evaluate differences in physical performance. The goal is to understand how frailty impacts transplant outcomes and patient recovery.

Detailed Description

This longitudinal, prospective study focuses on assessing the role of physical frailty in patients undergoing evaluation for kidney transplantation using the Short Physical Performance Battery (SPPB). The study will enroll adult patients who are being assessed for kidney transplantation, including those who are deemed suitable and placed on the waiting list (Arm A) and those on dialysis who are considered unsuitable for transplant listing (Arm B).

Participants will undergo comprehensive SPPB assessments at baseline, during their evaluation process, and subsequently at annual follow-up intervals. For listed patients, the assessments will be performed upon initial evaluation, then annually while on the waiting list, and at 6 and 12 months following transplantation. For patients ineligible for the transplant list and on dialysis, the SPPB will be recorded at baseline and then annually, allowing cross-sectional comparison and understanding of their physical performance trajectory.

The primary objective is to evaluate changes in physical performance over time with the SPPB score, which ranges from 0 to 12. The scores will be used to categorize participants into frail, pre-frail, or non-frail groups, providing insights into the prevalence and evolution of frailty in this population.

Secondary objectives include comparing the baseline and follow-up SPPB scores between the two arms, correlating physical performance with post-transplant outcomes such as graft function and survival, and identifying potential predictors of frailty that could inform prehabilitation interventions.

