This study may inform future strategies to optimize physical function in kidney transplant candidates and improve clinical outcomes through targeted interventions addressing physical frailty.

Study Design:

1. Study Overview

This prospective cohort study aims to assess physical frailty using the Short Physical Performance Battery (SPPB) among patients undergoing kidney transplant evaluation. The study will track physical performance changes before listing, annually for those listed, and at 6 and 12 months post-transplant. A comparison will be made between patients on the transplant waiting list and those on dialysis who are not eligible for listing.

2. Study Design

- **Type:** Longitudinal, prospective cohort study.
- **Duration:** 3-5 years.
- **Participants:** Adult patients undergoing kidney transplant evaluation.

3. Objective

- **Primary Objective:** To assess changes in physical performance using SPPB scores before and after kidney transplantation.
- **Secondary Objective:** To compare SPPB scores between patients on the waiting list and those on dialysis not eligible for the list.

4. Methodology

Inclusion Criteria:

1. Adult patients (≥ 18 years) undergoing evaluation for kidney transplantation.
2. Patients on dialysis.
3. Ability and consent to participate.

Exclusion Criteria:

1. Non-adult patients.
2. Patients unable to provide informed consent.
3. Acute medical conditions prohibiting SPPB assessment.

Study Arms:

- **Arm A:** Patients eligible and listed for kidney transplantation.
- **Arm B:** Dialysis patients not suitable for the waiting list.

SPPB Assessment:

- Measurement of physical performance including:
 - Balance tests (side-by-side, semi-tandem, tandem stands)
 - Gait speed (over a short distance)
 - Repeated chair stands

Data Collection:

TRANSPLANT-NEPHROLOGY DEPARTMENT

- **Baseline:** During initial evaluation for kidney transplantation.
- **Follow-up:** Annually for listed patients; at 6 and 12 months post-transplantation.

5. Statistical Analysis

- **Sample Size:** Estimated 200 patients (100 per arm) to ensure sufficient statistical power.
- **Statistical Tests:**
 - Descriptive statistics for baseline characteristics.
 - Paired t-tests or Wilcoxon signed-rank tests for changes in SPPB scores.
 - Chi-square tests for categorical outcomes.
 - Mixed-effects models to analyze longitudinal SPPB score changes.
 - Kaplan-Meier analysis for survival outcomes related to frailty status.

6. Expected Outcomes

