TRANSPLANT-NEPHROLOGY DEPARTMENT

- **Data Recording:** All scores will be documented in the study database, ensuring consistency and reliability.

Additional Notes:

- Assessments should be performed by trained personnel to ensure consistency.
 - Patients will be allowed rest between components to prevent fatigue.
 - Adaptations will be made for patients with mobility aids, if necessary, but these will be noted.
-

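### The written SPPB point rules reach at most 8, not the stated 12, so no participant scored by them can be classed as robust/non-frail

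*Protocol*

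**What the plan says.** The Detailed Description bases the primary objective on "the SPPB score, which ranges from 0 to 12" and adds that "The scores will be used to categorize participants into frail, pre-frail, or non-frail groups". SPPB Assessment Procedure, under Methodology (Detailed), repeats the 0–12 range.

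Components and Scoring then gives the rules for the three parts:

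- **Balance**, maximum 4: side-by-side stand 0 or 1, semi-tandem stand 0 or 1, tandem stand 0 or 2.
- **Gait**, headed "Gait Speed (Maximum score: 4 points"): over 4.82 s scores 0; 3.00 to 4.82 s scores 1; under 3.00 s scores 2.
- **Chair stands**, headed "Repeated Chair Stands (Maximum score: 4 points"): over 16.7 s scores 0; 11.2 to 16.7 s scores 1; under 11.2 s scores 2.

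A note below the rules says that "the best possible score per sub-test is reached if the participant can perform the task within the ideal time" or balance parameters. Scoring Interpretation labels totals of 0–6 frail, 7–9 pre-frail, and 10–12 "Robust/Non-frail (Normal physical performance"). Section 5, Statistical Analysis, lists "Kaplan-Meier analysis for survival outcomes related to frailty status". On data capture, the Assessment Protocol says that "All scores will be documented in the study database".

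**The concern.** The headings give each timed test a maximum of 4, but the rules under them stop at 2. The component maxima, the point rules, the total range and the frailty cut-offs therefore cannot all hold.

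The SPPB is the only performance measure in the study, and both the primary and the secondary objective rest on it. If the printed rules are followed:

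- The non-frail group is empty by construction. Its prevalence cannot be estimated, and no one can be seen to move into it after transplantation.
- The survival analysis by frailty status loses one of the three groups that the protocol defines.
- The paired tests and mixed models for SPPB change still run, but on a score with fewer steps, a lower ceiling and different component weights from those stated.

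**Working it through.** All inputs come from Components and Scoring and Scoring Interpretation.

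**1. The stated maximum.** The component headings give 4 + 4 + 4 = 12. This agrees with the 0–12 range, so the headings, range and bands fit one another.

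**2. The maximum from the point rules.**

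| Component | Maximum in heading | Points awarded by the rules | Attainable maximum |
|---|---|---|---|
| Balance | 4 | (0 or 1) + (0 or 1) + (0 or 2) | 1 + 1 + 2 = 4 |
| Gait | 4 | 0, 1, 2 | 2 |
| Chair stands | 4 | 0, 1, 2 | 2 |
| **Total** | **12** | | **4 + 2 + 2 = 8** |

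The stated 12 cannot be reached from the rules.

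**3. Could rows be missing from the text?** Each timed test has one band above its upper cut-off, one between the cut-offs and one below the lower cut-off. Together they cover every completion time. A 3- or 4-point row could be added only by overlapping or splitting a printed band. Both tests show the same 0, 1, 2 pattern.

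**4. Which frailty classes can be reached?** Balance can take 5 values (0 to 4), gait 3 and chair stands 3, giving 5 × 3 × 3 = 45 combinations of component scores. Listing all of them gives:

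| Class | Stated totals | Attainable totals | Combinations |
|---|---|---|---|
| Frail | 0–6 | 0–6 | 41 |
| Pre-frail | 7–9 | 7, 8 | 4 |
| Robust/non-frail | 10–12 | none | 0 |

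The four pre-frail combinations (balance, gait, chair) are (3, 2, 2), (4, 1, 2), (4, 2, 1) and (4, 2, 2). These are counts of score patterns, not proportions of participants.

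**5. Particular cases under the printed rules.**

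- Best result on every test: 4 + 2 + 2 = 8, pre-frail.
- Full balance score and middle-band times on both timed tests: 4 + 1 + 1 = 6, frail.
- Tandem stand not held, all else best: (1 + 1 + 0) + 2 + 2 = 6, frail.
- Walk over 4.82 s, all else best: 4 + 0 + 2 = 6, frail.
- Chair stands over 16.7 s, all else best: 4 + 2 + 0 = 6, frail.

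For comparison, suppose each timed test could reach its stated 4. A single zero on the tandem stand, gait or chair stands would then allow totals up to 2 + 4 + 4 = 10, 4 + 0 + 4 = 8 and 4 + 4 + 0 = 8.

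**6. Tolerance and weighting.** On the attainable score, pre-frail means losing at most 8 − 7 = 1 point from the best performance. On a 12-point score it means losing 12 − 9 = 3 to 12 − 7 = 5 points. Balance makes up 4/8 = 50% of the attainable total, against 4/12 = 33% of the stated one.

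**7. Would correcting one component be enough?** If gait alone reached 4, the maximum would be 4 + 4 + 2 = 10, still short of 12. Both timed components need attention.

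**The case against.** The best counter-argument is that staff may not score from these tables. The protocol describes the components as scored on a standardized scale, refers to standardized procedures and asks for trained assessors. If staff use a standard form, the printed bands may be only a drafting slip, and the non-frail group would not be empty in the data. This stands as a limit on the consequence: the protocol does not show what is done in practice. It does not remove the contradiction, because a general reference to standard procedure does not override explicit point rules. Data scored another way would depart from the protocol, and two assessors could score the same performance differently over a study of 3–5 years.

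Three narrower points also have some force:

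- The 10, 8 and 8 comparison concerns cases that score zero on one item. A participant who scores zero on the present time cut-offs might not do so after the bands are reconciled.
- The protocol names scores for the database but does not say that raw times will be discarded. Their loss is a risk, not an established fact.
- The Kaplan-Meier line gives no number of groups; three comes from the frailty classification elsewhere. A comparison of frail with all others would still run, but with changed membership.

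The note on the best possible score does not help, since it defines no category worth 3 or 4 points. A separate analysis plan could not recover those points from recorded scores of 0 to 2 without the raw times.

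**Conclusion.** The concern holds. As written, the rules give a maximum of 8 against a stated 12, totals of 9 to 12 are unreachable, and the robust/non-frail band is empty. This follows from the protocol's own text and needs no outside figure.

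The consequences for the data assume that assessors follow the printed rules. In that case non-frail prevalence is 0% at every visit in both arms, a zero on the tandem stand, the walk or the chair stands forces the frail class, and the primary score runs from 0 to 8. The number of participants misclassified cannot be calculated, because it depends on their times, which the protocol does not give.

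This must be fixed: the error is in the scoring rule of the primary measure, and scores recorded without raw times may not be recoverable.

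**What to change.** - Reconcile the gait and chair-stand point bands, the component maxima, the 0–12 range and the frailty cut-offs against the scoring form of the instrument the sponsor uses, so that each timed component can reach its stated 4 and the total can reach 12.
- Apply the 0–6, 7–9 and 10–12 bands only to the corrected score.
- Record the raw walk time, chair-stand time and balance hold durations at every assessment, so that scores can be derived again and checked.
- State which scoring was used for any participant assessed before the correction. Rescore from raw times where they were kept.

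The cost is a protocol wording correction and a few fields on the case report form, with no added visits or tests. Where raw times were not kept, earlier scores may not be comparable with corrected ones, so the change is cheapest if made early.

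### The protocol commits to storing SPPB scores but not the measured gait and chair-stand times, although its scoring table contradicts itself and visits may need rescoring

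*Protocol*

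**What the plan says.** The Data Recording line under Assessment Protocol reads "All scores will be documented in the study database, ensuring consistency and reliability". It is the only statement about which SPPB results are stored; a later note adds that adaptations for mobility aids are noted. The protocol does not say whether measured times are kept or discarded.

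Components and Scoring defines both timed tests by a measured time: "Time to walk 4 meters (standardized corridor" for gait and "Time to rise from a chair 5 times" for chair stands. Each time is cut into three bands worth 0, 1 or 2 points, and the top bands are "< 3.00 seconds: 2 points" and "< 11.2 seconds: 2 points". The headings of the same two items give a higher ceiling: "Gait Speed (Maximum score: 4 points" and "Repeated Chair Stands (Maximum score: 4 points". The introduction to that section adds "The total SPPB score ranges from 0 to 12", and Scoring Interpretation has a non-frail category of 10-12. Each balance stance is scored as held for 10 seconds or not.

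The primary objective (section 3) is change in SPPB score from before to after transplantation. Section 5 plans paired tests and mixed-effects models on that score.

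**The concern.** What is stored is usually a matter for the case report form. Here the protocol itself makes it matter, because the score it promises to store comes from a table that has to be reconciled. A stored gait score of 0 says only that the walk took longer than 4.82 s, and a stored 2 only that it took less than 3.00 s. If the bands change, such points cannot be moved to the new scale without the seconds.

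The pre-transplant assessment is most exposed, because it cannot be repeated once the patient has been transplanted. A patient's baseline and follow-up could then sit on different scales, which would spoil the within-patient comparison that is the primary objective.

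A second, smaller cost is that banding hides change that has already been measured. The lowest gait band has no upper limit: a patient who slows from 5 s to 9 s (4/5 = 0.80 to 4/9 = 0.44 m/s) scores 0 both times.

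**Working it through.** **1. Reachable score from the printed table.**

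| Component | Stated maximum | Highest points printed |
|---|---|---|
| Balance | 4 | 1 + 1 + 2 = 4 |
| Gait | 4 | 2 |
| Chair stands | 4 | 2 |
| Total | 12 | 8 |

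Under the printed bands no patient can reach the 10-12 category. Either the bands or the maxima, range and categories must change.

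**2. Can stored points be converted?** A component with a maximum of 4 in whole points has five possible values, 0 to 4. The stored component has three. Three values cannot be mapped onto five without the underlying time.

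**3. Sensitivity lost on gait.** The protocol gives no gait mean, SD, expected gain, correlation or number transplanted, so all of these are assumptions: SD 0.25 m/s at both visits; mean before transplant 0.7, 0.9 or 1.1 m/s; true gain 0.08 m/s; 50 pairs; before-after correlation ρ of 0.5, 0.7 or 0.8; normal speeds; paired t-test at two-sided 5%.

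- Cut-points as speeds: 4/4.82 = 0.830 m/s and 4/3.00 = 1.333 m/s.
- Share in the zero band, Φ((0.830 − mean)/0.25): 70%, 39% and 14% for means 0.7, 0.9 and 1.1.
- Standardised change on raw speed, 0.08 / (0.25 × √(2(1 − ρ))): 0.08/0.250 = 0.32 at ρ = 0.5; 0.08/0.194 = 0.41 at ρ = 0.7; 0.08/0.158 = 0.51 at ρ = 0.8.
- Power, by simulation:

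| ρ | Raw speed | 0/1/2 bands (range over the three means) |
|---|---|---|
| 0.5 | about 60% | 34-40% |
| 0.7 | about 82% | 41-49% |
| 0.8 | about 94% | 46-56% |

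Relative efficiency is the squared ratio of the standardised change on bands to that on raw speed. It runs from about 0.30 to 0.58. On the effect-size scale the loss is 1 − √0.58 = 24% to 1 − √0.30 = 45%. On the sample-size scale the bands need 1/0.58 = 1.7 to 1/0.30 = 3.3 times as many pairs.

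**4. Check with a second model, covering chair stands as well.** This used log-normal times and a 5% improvement, SD of log time 0.25 or 0.35, ρ of 0.5, 0.7 or 0.85, gait medians of 3.0 to 6.0 s and chair-stand medians of 11.2 to 20 s, again all assumed. Over 54 scenarios the relative efficiency runs from 0.20 to 0.68, the standardised change shrinks by 17% to 55%, and 50% to 86% of patients stay in the same band.

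**The case against.** The strongest reply is that the recording line does not say that only scores are kept. Times may well be on worksheets or in the case report form, which are not shown, and protocols often leave such detail there. This stands. A reader might infer that the seconds are thrown away and that no visit can ever be rescored. The document does not support that: it is silent, and the consequence follows only if the times are not kept. What can be said is that the protocol commits to scores and to nothing finer.

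A reader might also infer that the timed tests lose most of their sensitivity. That is too strong. For gait the effect-size loss is 24-45%, and in the second model it exceeds half in only 2 of 54 scenarios. The figures concern single components, whereas the endpoint is the total. They also rest on the printed bands, which may change.

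Three further points stand:

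- The loss of sensitivity comes from the bands and from the choice of the score as endpoint. Storing seconds does not change the primary analysis, and an ordinal composite is a legitimate endpoint.
- Stances are scored as held or not, so the protocol does not show that hold times are taken as durations.
- If the table were reconciled by lowering the maxima and the range to fit the bands, stored points would remain usable.

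None of this removes the point. The protocol leaves open which way the table will be reconciled, and only stored times are safe under either outcome.

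**Conclusion.** The point holds as a cheap improvement that should be made, not as proof that data will be lost. The firm part needs no assumptions: the protocol commits only to scores, the table reaches 8 points against a stated 12, and three-level points cannot be turned into a finer score. The harm arises if the times are not kept and the bands are changed; it would then be irreversible for assessments already made, including the pre-transplant baseline. The document does not say whether any patient has been tested yet.

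The gain from analysing the times themselves is substantial for gait, but its size depends on assumptions the protocol does not supply: power of 60-94% against 34-56%, relative efficiency about 0.3 to 0.6. The loss for the total score should be smaller and has not been quantified.

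**What to change.** - Change the Data Recording rule so that raw gait time, raw chair-stand time and the result (or hold time) of each stance are stored at every visit, or unable with the reason.
- Derive points and total from these fields by program, so that a revised table can be applied to all visits alike.
- Reconcile the printed bands with the stated maxima, the 0-12 range and the frailty categories. Which of them should change is for the investigators to settle.
- Add gait speed and chair-stand time as continuous secondary outcomes in the planned mixed-effects model, with a rule fixed in advance for patients who cannot complete a test. Without such a rule, the weakest patients would drop out of these analyses.
- If any patient has already been tested, enter the times from source records where they exist.

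The cost is a few extra fields per visit and one or two added secondary analyses. Gait and chair-stand times are already measured, so no new test or visit is needed. The primary score analysis stays as planned.
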